4.3 Subject replacement

Discontinued subjects may be replaced by enrollment of additional subjects until approximately 120 subjects are enrolled.

5 TREATMENT OF SUBJECTS

Subjects will receive a single dose of IMP in one (study) eye. The IMP will be randomized as either AG-920 or Placebo. The study eye will be randomized as either right eye (OD) or left eye (OS). The single dose will be administered by the clinic staff as two drops in the study eye 30 seconds apart.

5.1 *Concomitant medications*

5.1.1 **Prohibited medications**

The list of prohibited medications provided below may not be comprehensive. Investigators are encouraged to consult with the Medical Monitor for a decision about proceeding if they have any questions or concerns about any medication.

The following medications are prohibited.

- systemic opioids or opiate analgesics within 30 days of randomization and during the study treatment day
- topical NSAIDs within 30 days of randomization and during the study treatment day
- Over-the-counter (OTC) artificial tear lubricant products within one hour preceding or following study medication, other than the tolerability test

As noted in the exclusion criteria (Section 4.2), individuals must refrain from contact lens wear on the Dosing and Anesthesia Testing Day.

5.1.2 **Allowed medications**

Other than the agents and/or times noted above, systemic therapy with agents is allowed.

Use of all medications should be documented on the appropriate CRF. Investigators are encouraged to contact the Sponsor for any questions regarding allowed medications. Judgment of continued study participation by the subject, and inclusion of this subject's subsequent visits in the safety and efficacy analysis will be made by the Sponsor.

All medications which the subject has taken within 30 days prior to screening and during the study will be recorded in the CRF. The name of the drug, dose, route of administration, duration of treatment and indication will be recorded for each medication. For combination products (e.g., Contac®), the brand name is required. For non-combination products, the generic name is desired. The use of routine ophthalmic diagnostic pharmaceutical agents (e.g., fluorescein and local anesthetic) will be allowed, and individual documentation not required.

5.2 *Female Subjects*

Female subjects of childbearing potential must not be pregnant or breastfeeding at Randomization. These subjects must have a negative urine pregnancy test at Screening in order to be eligible for the study.

Female subjects who are not of childbearing potential must meet at least one of the following criteria:

- At least 1 year since the last menstrual period
- Surgically sterile (tubal ligation, bilateral oophorectomy, salpingectomy, or hysterectomy)

- Congenitally sterile
- Diagnosed as infertile and not undergoing treatment to reverse infertility

6 STUDY PROCEDURES

6.1 General Procedures:

The study will consist of 1 or 2 clinic visits and 1 Follow-up Phone Call. All ocular assessments will be performed on both eyes. Subjects will be screened for entry (Visit 1) and randomized/treated at (Visit 2). Visit 1 and 2 may be on the same day. At randomization, subjects will receive a single dose of IMP (2 drops 30 seconds apart) in the study eye. Subjects will then have a safety Follow-up Phone Call 1-4 days (Days 2-5) following Visit 2.

6.2 Re-screening Procedures:

A subject who is first designated as a screen failure prior to being randomized will be allowed to rescreen one additional time 7-30 days later.

6.3 Visit 1 (Screening) – Day -2 to 0/1

Visit 1 may be combined with Visit 2 in order to accommodate clinic logistics. If both visits are combined, Visit 1 will last anywhere from 1-3 hours. If topical anesthetic drops are used to assess IOP, subject must wait at least 1 hour before IMP treatment. Topical anesthetic drops may cause a mild stinging or burning sensation upon instillation.

The following procedures will be performed in the following suggested order at Visit 1. All ocular tests at this and all visits will be performed in both eyes (with the exception of conjunctival pinching):

- Obtain written informed consent to participate before any study-required screening assessments have been conducted
- Collect demographics (sex, year of birth, race, ethnicity)
- Collect systemic medical history and ocular medical history
- Review of prior and concomitant medications (including ocular medications)
- Study technician to instill a drop of an Over-The-Counter artificial tear. At the opinion of the Investigator/Study Technician, only individuals who tolerate this drop, will be enrolled.
- Perform urine pregnancy test (UPT) on women of childbearing potential (see Appendix 1).
- Measure Best Corrected Visual Acuity (BCVA) (see Appendix 1)
- Perform slit lamp biomicroscopy and external eye exam (see Appendix 1)
- Measure IOP (see Appendix 1)
- Verify subject eligibility based on Inclusion/Exclusion requirements
- Schedule subject to return for Visit 2 if Visit 1 and 2 are not performed on the same day.

6.4 Visit 2 (Randomization/Treatment) – Day 1

Visit 2 must occur within 3 days of Visit 1 (Screening) if it is not performed on the same day as Visit 1. As noted in Section 6.3, Visit 1 and Visit 2 may be performed on the same day for clinic logistics. If a topical anesthetic is used to measure IOP at Screening (Visit 1), there must be at least a 1-hour interval post-anesthetic drops prior to treatment with IMP. At Visit 2, subjects are expected to be in the clinic for approximately 60 minutes post dose.

6.4.1 Pre-dose

The following procedures will be performed in the following order at Visit 2, if Visit 1 was not performed on the same day:

- Re-verify subject eligibility based on Inclusion/Exclusion requirements.
- Review of any changes in health (medical history and AEs) or concomitant medications (including ocular medications) if Visit 2 is not combined with Visit 1

6.4.2 IMP Treatment

- Once qualification is confirmed, subject will be randomized.
 - Subject will be randomly assigned to receive a single dose of either AG-920 or Placebo
 - Subject will be randomly assigned to receive the IMP dose into one eye only (study eye)
 - [REDACTED]
- Retrieve IMP kit number assigned and confirm study eye
- Remove foil pouch from kit and remove 1 vial from foil pouch
- Open vial top
- Administer 1 drop of IMP to the study eye
- Wait 30 seconds
- Administer a second drop of IMP to the same study eye from the same vial
- Assess for adverse events
- Return used vial to foil pouch and retain used vial and remaining 4 unused vials for accountability

6.4.3 Post Treatment and Pinch Test

- [REDACTED] forceps will be used to “pinch” the [REDACTED] conjunctiva of the study eye at the following timepoints. Details on the pinching method will be provided separately:
 - **20 seconds following complete dose administration** (second drop of IMP)
 - **40 seconds following dose administration**
 - **60 seconds following dose administration**
 - **5 minutes following dose administration**
- Immediately following EACH pinch test, subjects will be asked “Was that painful” “Yes” or “NO.” It should be explained to subjects that the feeling of pressure is NOT to be judged as pain. [REDACTED]
[REDACTED].

All subjects are pinched at 20, 40, 60 seconds and 5 minutes post dose. If the subject feels no pain at 5 minutes, the subject will be considered “anesthetized.” Pinching of anesthetized subjects will continue at 10 minutes and EVERY FIVE MINUTES for up to 30 minutes or until pain resumes. Once pain resumes, pinching is stopped.

If the subject experiences pain at 5 minutes, pinching will be concluded and this subject will be considered to NOT have reached anesthesia at 5 minutes.

Within 15-60 minutes after the last pinch test, the following examinations will be performed

- BCVA
- Perform slit lamp biomicroscopy and external eye exam
- Assess for adverse events
- Schedule Follow-up Phone Call between Day 2-5 (1-4 days following dosing).

Windows: Times will be measured to the nearest minute with the exception of the 20, 40 and 60 second time points. Those should be recorded to the second. Times up to 5 minutes post 2nd instillation should be followed. Investigators are allowed a window of \pm 1 minute at the 10 minute time point, and \pm 2 minutes at subsequent time points.

6.5 Follow-Up Phone Call (Day 2-5)

Subjects will receive a phone call from site staff between Days 2-5, which is 1-4 days (24-96 hours post-dose) following treatment with IMP. Subjects will be asked about

- AEs
- Changes to concomitant medications

If there are any ongoing adverse events, the subject will be instructed to return to the investigator's office for appropriate evaluation. If there are no ongoing adverse events, the subject will be considered completed.

Subjects will be thanked for their participation and released to follow their normal standard of care.

6.6 Unscheduled visits

To ensure subject safety during the trial, any subject who requires additional follow-up during the study for any reason (that does not fall on a scheduled study visit) should have that visit recorded as an Unscheduled Visit.

6.7 COVID-19 Pandemic Accommodations

This study may be conducted during the COVID-19 pandemic. As a result, American Genomics is providing guidance to Investigators on how to modify the current protocol based on [guidance documents from the FDA](#) and other regulatory authorities. The objective of these potential modifications is to ensure the safety of trial participants and clinic staff, maintain compliance with good clinical practice (GCP), and minimize the risks to trial integrity during the COVID-19 pandemic.

To ensure the safety of trial participants and to minimize or eliminate hazards as a result of COVID-19 pandemic, the following alternative processes and procedures may be implemented when necessary:

1. Depending on local COVID-19 prevalence and prevailing local ordinances and guidances, some screening visit procedures may be conducted by telephone, by video conferencing, or by remote staff in the subject's home.
2. The Randomization/Treatment Visits cannot be done by telephone or video conferencing and must be completed at the investigative site, if it is safe and feasible, per Investigator's judgment.

3. Site specific accommodations should be implemented per state and local guidances possibly including social distancing or personal protective equipment (PPE) requirements.
4. Remote monitoring visits of clinical trial data may be implemented.

7 ASSESSMENT OF EFFICACY¹

Assessments of efficacy will be as follows:

- **Assessment of pain questionnaire following conjunctival pinch.**

The timing of this assessment is provided in Section 6.4.3.

8 ASSESSMENT OF SAFETY

8.1 *Specification of safety parameters*

The assessment of safety and tolerability will be evaluated by:

- BCVA (ETDRS)
- Biomicroscopy and external eye exam of anterior segment including evaluation of cornea, conjunctiva and anterior chamber.
- AEs (post treatment)
- AEs will be collected at every visit. See Section 8.3 for details on collection and reporting of AEs.

Screening only:

- Intraocular pressure
- Urine pregnancy test for females of childbearing potential

8.2 *The methods and timing for assessing, recording, and analyzing safety parameters*

Methods may be found in Table 1 and Appendix 1.

8.3 *Adverse events²*

All AEs occurring after the first dose of IMP and throughout the remainder of the study period (Follow-up Phone Call) will be considered TEAEs and must be documented on the relevant Electronic Data Capture (EDC) pages and in the source documents. Whenever possible, the diagnosis, if available, and not the symptoms should be reported as the AE. AEs and Serious Adverse Events (SAEs) will be coded according to the Medical Dictionary for Regulatory Activities (MedDRA).

Documentation of adverse events/adverse reactions includes start date and stop date, severity, action(s) taken, seriousness and outcome.

² Note: This section is referenced to 21 CFR 312.32 (IND safety reports), updated as per “Investigational New Drug Safety Reporting Requirements for Human Drug and Biological Products and Safety Reporting Requirements for Bioavailability and Bioequivalence Studies in Humans (Fed Reg 2010: 75 (188): 59935-59963).

8.3.1 Adverse Event (AE) definitions

An *AE* is any untoward medical occurrence in a subject or clinical investigation subject, temporally associated with the use of a medicinal product, whether or not considered related to the medicinal product.

Note: An AE can therefore be any untoward or unfavorable medical occurrence in a human subject, including any abnormal sign (for example, abnormal physical exam or laboratory finding), symptom, or disease, temporally associated with the subject's participation in the research, whether or not considered related to the subject's participation in the research.

Any untoward or unfavorable medical occurrence in a human subject, including any abnormal sign (for example, abnormal physical exam or laboratory finding), symptom, or disease, temporally associated with the subject's participation in the research, whether or not considered related to the subject's participation in the research will be documented.

Events meeting the definition of an AE include:

- Exacerbation of a chronic or intermittent pre-existing condition including either an increase in frequency and/or intensity of the condition
- New conditions detected or diagnosed after study drug administration even though it may have been present prior to the start of the study
- Signs, symptoms, or clinical sequelae of a suspected interaction
- Signs, symptoms, or clinical sequelae of a suspected overdose of either study drug or a concomitant medication (overdose *per se* will not be reported as an AE/SAE).

Events that do **not** meet the definition of an AE include:

- Medical or surgical procedure (e.g., endoscopy, appendectomy); the condition that leads to the procedure is an AE
- Situations where an untoward medical occurrence did not occur (social and/or convenience admission to a hospital)
- Anticipated day-to-day fluctuations of pre-existing disease(s) or condition(s) present or detected at the start of the study that do not significantly worsen
- The disease/disorder being studied, or expected progression, signs, or symptoms of the disease/disorder being studied, unless rescue medication or other medical treatment is required.

8.3.1.1 *Life-threatening adverse event or life-threatening suspected adverse reaction.*

An adverse event or suspected adverse reaction is considered "life-threatening" if, in the view of either the Investigator or Sponsor, its occurrence places the subject at immediate risk of death. It does not include an adverse event or suspected adverse reaction that, had it occurred in a more severe form, might have caused death.

8.3.1.2 *Suspected adverse reaction*

Suspected adverse reaction means any adverse event for which there is a reasonable possibility that the drug caused the adverse event. For the purposes of IND safety reporting, "reasonable possibility" means there is evidence to suggest a causal relationship between the drug and the

adverse event. Suspected adverse reaction implies a lesser degree of certainty about causality than adverse reaction, which means any adverse event caused by a drug.

8.3.1.3 Unexpected adverse event or unexpected suspected adverse reaction.

An adverse event or suspected adverse reaction is considered “unexpected” if it is not listed in the Investigator brochure or is not listed at the specificity or severity that has been observed; or, if an investigator brochure is not required or available, is not consistent with the risk information described in the general investigational plan or elsewhere in the current application, as amended. For example, under this definition, hepatic necrosis would be unexpected (by virtue of greater severity) if the investigator brochure referred only to elevated hepatic enzymes or hepatitis. Similarly, cerebral thromboembolism and cerebral vasculitis would be unexpected (by virtue of greater specificity) if the Investigator brochure listed only cerebral vascular accidents. “Unexpected,” as used in this definition, also refers to adverse events or suspected adverse reactions that are mentioned in the Investigator brochure as occurring with a class of drugs or as anticipated from the pharmacological properties of the drug, but are not specifically mentioned as occurring with the particular drug under investigation.

Note: Any medical condition present prior to administration of the masked study medication which remains unchanged or improved should not be recorded as an adverse event at subsequent visits.

8.3.2 Serious Adverse Event (SAE) definitions

An *SAE* is an AE that:

- Results in death.
- Is life-threatening (an AE is life-threatening if the subject was at immediate risk of death from the event as it occurred, i.e., it does not include a reaction that might have caused death if it had occurred in a more serious form).
- Requires or prolongs inpatient hospitalization. Complications occurring during hospitalization are AEs or SAEs if they cause prolongation of the current hospitalization. Hospitalization or prolonged hospitalization for elective treatment of a pre-existing non worsening condition is not, however, considered an AE.
- Results in persistent or significant disability/incapacity. (An AE is incapacitating or disabling if it results in a substantial and/or permanent disruption of the subject’s ability to carry out normal life functions).
- Is a congenital anomaly/birth defect.
- Is an important medical event that may jeopardize the subject or may require medical intervention to prevent one of the outcomes listed above.

Medical and scientific judgment is required to decide if prompt notification is required in situations other than those defined for SAEs above. This can include an AE that suggests any significant hazard, contraindication, adverse event, or precaution that may be associated with the use of the IMP.

8.3.2.1 Recording an AE and/or SAE including Onset Date, End Date

When an AE/SAE occurs, it is the responsibility of the investigator to review all documentation (eg, hospital progress notes, laboratory reports, and diagnostics reports) related to the event. The investigator will then record all relevant AE/SAE information in the CRF.

If an AE starts but does not end before the final visit, the Investigator must make a reasonable effort to establish the outcome and the end date of the AE. If this is not possible (e.g., because the AE is still ongoing) or the subject is lost to follow-up, there will be no end date for the AE and the status will be recorded as “ongoing.” For all AEs that resolve, resolve with sequelae, or have a fatal outcome, an end date must be provided.

The investigator will attempt to establish a diagnosis of the event based on signs, symptoms, and/or other clinical information. Whenever possible, the diagnosis (not the individual signs/symptoms) will be documented as the AE/SAE.

8.3.2.2 Assessment of Causality

Every effort will be made by the Investigator to assess the relationship of the AE, if any, to the IMP. Causality should be assessed as unrelated or related using the categories defined in Table 2.

Table 2: AE Assessment of Causality

Unrelated:	
• Clinical event with an incompatible time relationship to IMP administration, and that could be explained by underlying disease or other drugs or chemicals or is incontrovertibly not related to the IMP, or• Clinical event whose time relationship to IMP makes a causal connection improbable, but that could plausibly be explained by underlying disease or other drugs or chemicals.
Related:	
• Clinical event with a reasonable time relationship to IMP, but that could also be explained by concurrent disease or other drugs or chemicals, or• Clinical event with a reasonable time relationship to IMP and is unlikely to be attributed to concurrent disease or other drugs or chemicals, or• Clinical event with plausible time relationship to IMP, and that cannot be explained by concurrent disease or other drugs or chemicals.

Abbreviations: AE=Adverse Event; IMP=investigational medicinal product

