1.2 Potential Risks and benefits to human subjects

Minimal risks are expected with AG-920.

Expected risks for subjects may include a temporary mild to moderate stinging or burning sensation upon instillation of the investigational medical product (IMP). Temporary mild hyperemia may also occur following instillation. For any additional information on AG-920 use, please refer to the [Investigator's Brochure](#).

As this study is to be conducted in healthy subjects, there is no anticipated benefit other than the possibility that a subject's participation in the present study may help others in the future to have more options for local anesthesia before ophthalmic procedures.

Adverse events (AEs) not reported in previous clinical trials but present among subjects in this clinical trial will be communicated to Investigators and to ethics committees or Institutional Review Board (IRBs) in accordance with local regulations.

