### **5.3 Adverse Events**

An overall summary of AEs reported in this study will be provided in Table 4.1.1 for study participants and in Table 4.1.2 for the safety population. The incidences of subjects reporting pre-treatment AE will be reported in Table 4.2.1 for the pre-randomization period and in Table 4.2.2 for the treatment-emergent AEs by treatment. Those treatment-emergent AE by preferred terminology that are reported by more than 5% of subjects in any treatment will be tabulated in Table 4.2.3.

Incidences of subjects reporting treatment-emergent AEs (TEAEs) will also be tabulated by treatment for the TEAEs associated with the study eye in Table 4.2.5 and for the TEAEs associated with non-study eye in Table 4.2.6.

Incidences of subjects reporting treatment-emergent AEs will also be tabulated by onset time (on-dosing day vs. off-dosing day) in Table 4.3.1 for all TEAEs, and in Table 4.3.2 for the TEAEs associated with the study eye, and in Table 4.3.3 for the TEAEs associated with non-study eye.

The severity of the treatment-emergent AEs and the relationship to the investigational product will be summarized in Table 4.4.1.

Treatment-emergent AEs associated with early terminations and serious AEs will be summarized by preferred term, respectively, in Table 4.4.2 and Table 4.4.3 for all TEAEs, in Table 4.4.4 and Table 4.4.5 for the TEAEs associated with the study eye, and in Table 4.4.6 and 4.4.7 for the TEAEs associated with the non-study eye.

Details of AEs associated with both study and non-study eyes will be listed for each subject (Listing 7)

Details of AEs associated with early terminations will be listed for each subject (Listing 8). SAEs, including deaths, will be listed for each event (Listing 9).

Narratives will be presented for all deaths, non-fatal serious adverse events, and subjects withdrawn due to adverse events.

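### AE causality is judged only against the drop, so conjunctival events from the 4 to 9 forceps pinches may be scored as drug-related; a masked relation-to-pinch field would separate them

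*Protocol*

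**What the plan says.** Protocol section 8.3.2.2 sets a two-level scale for relationship to the study drug: "Causality should be assessed as unrelated or related using the categories defined in Table 2".

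Table 2 has three routes to Related, and each opens with reasonable or plausible timing. The first applies even when a rival cause exists: "Clinical event with a reasonable time relationship to IMP, but that could also be explained by concurrent disease or other drugs or chemicals". The third is "Clinical event with plausible time relationship to IMP, and that cannot be explained by concurrent disease or other drugs or chemicals".

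There are two routes to Unrelated. One requires an incompatible time relationship and then adds that the event "could be explained by underlying disease or other drugs or chemicals or is incontrovertibly not related to the IMP". The other is "Clinical event whose time relationship to IMP makes a causal connection improbable, but that could plausibly be explained by underlying disease", or by other drugs or chemicals.

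Protocol section 6.4.3 has every subject pinched on the conjunctiva of the study eye at 20, 40 and 60 seconds and at 5 minutes after the second drop. Subjects with pain at 5 minutes stop there. For the rest: "Pinching of anesthetized subjects will continue at 10 minutes and EVERY FIVE MINUTES for up to 30 minutes or until pain resumes".

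Protocol section 1.2 says of the drop: "Temporary mild hyperemia may also occur following instillation".

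The causality result feeds the related/unrelated summaries in protocol section 9.4.8, SAP section 2.9.3 and SAP section 5.3: "The severity of the treatment-emergent AEs and the relationship to the investigational product will be summarized in Table 4.4.1".

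**The concern.** The only rival causes that Table 2 names are disease and other drugs or chemicals. The most obvious rival cause of a conjunctival event in this trial is the forceps, and no visible text asks the investigator about it.

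Safety and tolerability of the drop is a stated objective. If pinch trauma is recorded as related to the drop, the related-AE summaries describe drop plus procedure in both arms. Because response governs how many pinches a subject receives, the error may also differ between arms.

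The schedule offers little to separate the two causes afterwards. Post-dose biomicroscopy comes only 15 to 60 minutes after the last pinch. Between dosing and the first pinch there is only an AE query. The non-study eye is neither dosed nor pinched, so it cannot tell one cause from the other.

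**Working it through.** **1. How a pinch-site event passes through Table 2.** Take a red spot on the conjunctiva, seen minutes after dosing and caused by the forceps.

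- *Related, first route:* the timing is reasonable. This route tolerates another explanation, so a rival cause does not remove the event from Related.
- *Related, second and third routes:* the timing is reasonable or plausible, and neither disease nor another drug explains the spot. Both are met literally.
- *Unrelated, second route:* the timing does not make a link improbable, and neither disease nor a drug explains the spot. Not met.
- *Unrelated, first route:* the clause on being incontrovertibly unrelated can be read two ways. If it depends on incompatible timing, it fails minutes after dosing. If it stands alone, a clear forceps mark could qualify. Hyperemia could hardly meet so high a bar, because section 1.2 lists it as an effect of the drop.

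So a non-specific sign tends towards Related, while an obvious forceps injury could go either way.

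**2. Design rates.** The documents give 60 per arm, 15% response on placebo and a 25-point difference (protocol 9.2, SAP 2.5), hence 40% on AG-920. The plan's power figure reproduces with the chi-square test without continuity correction:

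- mean proportion = (0.15 + 0.40)/2 = 0.275
- null SE = √(2 × 0.275 × 0.725/60) = 0.0815
- alternative SE = √((0.15 × 0.85 + 0.40 × 0.60)/60) = 0.0783
- z = (0.25 − 1.96 × 0.0815)/0.0783 ≈ 1.15, giving power of 87.55% against the stated 88%

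This point does not bear on the power. It only borrows the two response rates.

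**3. Pinches per subject.** Four are fixed. Responders have k further pinches, with k from 1 (pain back at 10 minutes) to 5 (10, 15, 20, 25 and 30 minutes). That gives 4 for a non-responder and 5 to 9 for a responder. The mean is 4 + r × k, where r is the response rate.

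| k | AG-920 (r = 0.40) | Placebo (r = 0.15) | Ratio |
|---|---|---|---|
| 1 | 4.40 | 4.15 | 1.06 |
| 5 | 6.00 | 4.75 | 1.26 |

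This uses the same k in both arms. If AG-920 responders stayed numb longer than placebo responders, the gap could reach 6.00 against 4.15. In the opposite extreme it would reverse, at 4.40 against 4.75.

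**4. Illustration of the lean between arms.** The documents give no pinch-injury rate. Assume an independent risk q per pinch, the same k in both arms, and no drug effect on injury. The proportion of subjects with at least one pinch injury is

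(1 − r) × [1 − (1 − q)^4] + r × [1 − (1 − q)^(4 + k)].

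| q (assumed) | k = 1: placebo, AG-920 (difference) | k = 5: placebo, AG-920 (difference) |
|---|---|---|
| 0.5% | 2.06%, 2.18% (0.12 points) | 2.35%, 2.96% (0.61 points) |
| 1% | 4.08%, 4.32% (0.24 points) | 4.65%, 5.82% (1.18 points) |
| 2% | 8.04%, 8.50% (0.46 points) | 9.09%, 11.31% (2.22 points) |
| 5% | 19.16%, 20.18% (1.02 points) | 21.31%, 25.92% (4.61 points) |

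At q = 1% and k = 5, this is 2.79 against 3.49 subjects in 60, a difference of 0.70 of a subject. In every row the level common to both arms is larger than the difference between them.

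**The case against.** **The trial is randomized and vehicle-controlled.** Every subject has the same four pinches through 5 minutes. Protocol section 9.4.8 compares each AE term between arms by Fisher's exact test without restricting it to related events, and SAP section 5.3 tabulates treatment-emergent AEs by arm, with separate tables for the study eye and the non-study eye. *This stands.* A reader might infer that the related-AE table hides what the drop does. The documents do not support that, because the all-causality contrasts remain and do not use the causality scale.

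**Table 2 does not force a forceps injury into Related.** A reader might infer that only disease and other drugs can count as alternatives, so that every pinch injury must be scored as related. The incontrovertibly-unrelated clause is not tied to disease or drugs and may stand alone. *This stands*, and it limits the point to events that may be misattributed.

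**The imbalance in pinches comes from section 6.4.3, not from Table 2.** It would affect the all-causality comparison under any causality scale. *This stands.* What Table 2 adds is the drug-related label on those events. Any excess on AG-920 would also make the drop look less safe, so the error is conservative for a safety claim.

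**Absence cannot be shown.** Pinch details are supplied separately, Appendix 1 is largely redacted, and the CRF and table shells are not shown. A procedure field may exist. *This stands* as a limit on the point.

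**Conclusion.** The point holds as a cheap improvement to the safety reporting. In the visible plan, causality is assessed only against the study drug, mainly by timing, and no study procedure is named. Conjunctival events from pinching may be scored as related to the drop in both arms, and for non-specific signs such as hyperemia this is likely.

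The main effect is on how related AEs are read in both arms. The lean against AG-920 is secondary. At the design rates, with equal durations of numbness in responders, AG-920 subjects receive 6% to 26% more pinches. Under assumed risks of 0.5% to 5% per pinch, the difference in subjects with a pinch injury is 0.1 to 1.0 points with one extra pinch per responder and 0.6 to 4.6 points with five. The true size is unknown because the documents give no injury rate.

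The primary endpoint and sample size are untouched.

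**What to change.** 1. Add one AE field, relation to the conjunctival pinch procedure (yes/no), completed by the investigator while masked and alongside the existing judgement of relation to the study drug.
2. State in Table 2 whether the clause on being incontrovertibly unrelated stands alone or depends on incompatible timing.
3. In SAP section 2.9.3 and Table 4.4.1, tabulate relation to the drug and relation to the pinch separately by arm, with the number of pinches received.

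Simply adding study procedures to the rival causes in both Table 2 categories would not work. The first Related route keeps an event Related even when something else could explain it, and the timing-based routes to Unrelated would still fail.

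The cost is one CRF field, one clarified sentence and extra table columns. Attribution between drop and pinch will remain a judgement for some events. It should be recorded at the time, since it cannot be rebuilt reliably after database lock. If the CRF already has such a field, the protocol and SAP text need only be aligned with it.
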